## 1.0 Study Summary

Study Title	An integrated nutrition intervention through the Part C Early Intervention Services to promote healthy eating habits for children with ASD
Study Design	Randomized controlled trial
Primary Objective/Purpose	Aim 1: To refine the Autism Eats manual and intervention materials. Aim 2: To evaluate the feasibility and preliminary efficacy of Autism Eats in improving dietary intake and mealtime behaviors of children with ASD.
Secondary Objective(s)/Purposes	To explore whether child weight status differs between Autism Eats and enhanced usual care groups at 5-month follow-up assessment.
Research Intervention(s)	Autism Eats – Early childhood nutrition intervention
ClinicalTrials.gov NCT #	NCT05194345
Study Population	Early intervention providers and parent-child dyads (child aged 0-36 months clinically diagnosed with ASD)
Sample Size	146 individuals Aim 1: 10 EI providers, 10 parents Aim 2: 30 EI providers, 48 parent-child dyads (48 parents and 48 children)
Study Duration for individual subjects	Aim 1: up to 3 hours per participant to review manual and provide feedback. Aim 2: Parent-child dyads : The Autism Eats intervention group will spend about 8.5 hours over 5 months (baseline, post intervention, and 5-month follow-up assessments are 30 minutes each, 25-30 minutes weekly sessions for up to 10 weeks, two 25-30 minutes monthly booster sessions, and a 60-minute exit interview), and the We Can! EUC control group will spend about 3 hours over 5 months (baseline, post intervention, and 5-month follow-up assessments are 30 minutes each, one 25-30 minute nutrition session, and a 60-minute exit interview). EI provider : The Autism Eats intervention group EI provider will spend about 12 hours over 5 months (two 90-minutes training sessions, 25-30 minutes weekly sessions for up to 10 weeks, two 25-30 minutes monthly booster sessions, 10-minute fidelity checklist completion

	after each session, and a 60-minute exit interview), and the We Can! EUC control group EI provider will spend about 4.5 hours over 5 months (two 90-minutes training sessions, one 25-30 minutes session, 1-2-minute written material distribution at their 9 weekly EI sessions, and a 60-minute exit interview).

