
Aim 1. To refine the Autism Eats manual and intervention materials.

Aim 2. To evaluate the feasibility and preliminary efficacy of Autism Eats in improving dietary intake and mealtime behaviors of children with ASD.

2a. Test the feasibility of enrollment, implementation, and evaluation of Autism Eats.

2b. Assess the preliminary efficacy of Autism Eats for improving child dietary intake and mealtime behaviors.

Exploratory Aim. To explore whether child weight status differs between Autism Eats and EUC groups at 5-month follow-up assessment.

2.2 Hypothesis 1: We hypothesize that Autism Eats will be feasible and well-received by EI providers and parent-child dyads.

Hypothesis 2: We hypothesize that there will be differences in children dietary food intakes, variety, diet quality, and mealtime behaviors between children who participate in Autism Eats and those in the EUC groups at post-intervention and 5-month follow-up from baseline.

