Exploratory Aim. We will explore whether weight status of children are different between Autism Eats and EUC groups at 5-month follow-up assessment. Descriptive statistics and visual inspection will be used to summarize weight status by group and effect sizes will be computed. Similar to the analysis of the primary outcomes, we will conduct nonparametric analysis to compare the changes in weight status at 5-month follow-up between Autism Eats and EUC groups. Note that parent BMI will be included as a covariate in the analysis.

16.2 Data will be collected and maintained in accordance with legal and ethical standards and will be centrally stored in a master database. RedCap is a secure web application for research studies in HIPAA compliant environments, which will be used to collect data, except the dietary intake data that will be collected through the ASA24 online system. RedCap will allow for data to be entered and uploaded to a central, secure database, while prohibiting access outside USF. Providers and parents will be emailed a link to the RedCap-based surveys.

Only principal investigator and study staff members will have access to files containing identifiers such as contact information of study participants (providers and parent-child dyads). These files will be stored in an encrypted form in a password protected secure database. These files will be used only for data collection.

The collected data will be deidentified. Participants' information that individuals can be identified with will be removed from the study data files. The deidentified data will be stored as study data files in a password protected USF computer in a locked USF office.

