Autism Eats and EUC groups are balanced through randomization in terms of demographic variables at baseline. For each outcome variable, we will use boxplots and scatterplots with confidence intervals to visually inspect the changes across pre-intervention, post-intervention, and 5-month follow-up by group along with descriptive statistics. Also, nonparametric longitudinal analysis will be conducted for each outcome variable with time as a within-subject factor and treatment condition as a between-subject factor to examine the difference in changes between Autism Eats and EUC groups. (See Table 4).

Exploratory Aim. We will explore whether weight status of children are different between Autism Eats and EUC groups at 5-month follow-up assessment. Descriptive statistics and visual inspection will be used to summarize weight status by group and effect sizes will be computed. Similar to the analysis of the primary outcomes, we will conduct nonparametric analysis to compare the changes in weight status at 5-month follow-up between Autism Eats and EUC groups. Note that parent BMI will be included as a covariate in the analysis.

Table 4. Efficacy Outcomes

Outcomes	Measures / Expected Outcomes	Time
Dietary intake	3-day food records (ASA24 TM) / Food intakes (e.g., fruit and vegetables ↑), daily food variety ↑, diet quality (e.g., HEI fruit ↑, vegetables ↑, plant protein ↑)	T1, 2,3
Mealtimes behaviors	Brief Autism Mealtime Behavior Inventory ¹⁶ via REDCap / Problematic behaviors ↓.	T1,2,3
Weight status (height and weight)	A stadiometer/ruler and a scale; birth to 36 months, weight-for-length%tile based on the CDC growth chart. ¹⁷ BMI for parents	T1 & 3
Demographics	A survey through the REDCap.	T1
Health conditions	Family history of ASD and comorbid health conditions such as epilepsy, sleep disorders, and anxiety disorders through the REDCap.	T1

Biological variables. Sex: Given the sex difference in ASD prevalence, in addition to the primary data analyses as described above, data distributions will be analyzed by sex. We will then explore how male and female students respond to our intervention differently through qualitative interviews with selected sub-samples. Recommendations will be created to address any sex differences.

Genetic factors: Family history of ASD and parent BMI will be measured and considered as covariates.

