Potential confounding factors to be considered in the analytic models. Parent age, sex, race/ethnicity, baseline child's weight status, parent education, and family income.

Examine demographic variations in response to the Autism Eats intervention. Correlation will be used to examine associations between demographic variations (age, sex, race/ethnicity, SES, and baseline weight status) outcomes of the Autism Eats (food intakes, food variety, diet quality, mealtime behaviors, and weight percentile).

Attrition and Missing Data. See Benchmarks for feasibility (Table 3). We aim < 20% dropout due to study withdrawal. Every effort will be made to prevent dropouts/missing data, and to complete relevant assessments for participants who drop out or are withdrawn, including reasons why the intervention was ended. To handle the dropout problem in this trial, we will first analyze data to see whether dropout was related to certain baseline measures and demographic variables. We will report the dropout rate and compare the distributions of baseline measures and demographic variables.

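### The exploratory weight aim asks about status at 5 months, its only planned test compares changes, its effect size is tied to neither, and no adjustment for the baseline value is fixed.

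*SAP*

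**What the plan says.** **The question.** Protocol 1.0 gives the secondary objective as "To explore whether child weight status differs between Autism Eats and enhanced usual care groups at 5-month follow-up assessment". Protocol 2.0 repeats it as the Exploratory Aim. Protocol 16.1 opens its analysis paragraph with "We will explore whether weight status of children are different between Autism Eats and EUC groups at 5-month follow-up assessment", and the SAP paragraph opens in the same way. None of these mentions baseline.

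**The test.** The same paragraph in Protocol 16.1 then says "we will conduct nonparametric analysis to compare the changes in weight status at 5-month follow-up between Autism Eats and EUC groups"; the SAP likewise plans to "compare the changes in weight status at 5-month follow-up between Autism Eats and EUC groups". Table 4 in both documents schedules weight at T1 and T3 only, so the change can only be T3 minus T1. The child measure is "weight-for-length%tile based on the CDC growth chart".

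**The effect size.** The SAP says "Descriptive statistics and visual inspection will be used to summarize weight status by group and effect sizes will be computed". It does not say whether the effect size refers to T3 status or to change.

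**Covariates.** Parent BMI is to be included. Baseline child weight status appears only in the SAP list of potential confounders for consideration: "Parent age, sex, race/ethnicity, baseline child's weight status, parent education, and family income". The planned check of baseline balance names demographic variables only.

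**Size.** Protocol 5.1 has 24 dyads per arm. The SAP has 30 with 1:1 allocation, which is 15 per arm if read as dyads.

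**The concern.** A between-arm difference in T3 weight status and a between-arm difference in change are two different calculations on the same children. If the plan does not say which one answers the aim, the effect size can be computed either way once the data are in hand. The two ways can have quite different standard errors. For its key outcomes the SAP says that the pilot's yield is variances and effect sizes, so an effect size from an undefined contrast is of little use for planning a later trial.

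Nothing else in the plan settles the matter. Baseline adjustment would bring the two calculations together, but it is optional. The nonparametric method that is to carry parent BMI as a covariate is not named. A chance imbalance in baseline weight might not be looked for, because the balance check is confined to demographic variables.

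**Working it through.** The documents give no power, standard deviation, alpha or effect size for weight, so there is no figure to reproduce.

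**Inputs from the documents.** n = 24 per arm (Protocol 5.1) or 15 (SAP); weight at T1 and T3; the outcome is a percentile.

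**Assumptions, not in the documents.** Normal z-scores with equal SD at T1 and T3; T1-T3 correlation r from 0.5 to 0.9; no other covariates; percentiles spread evenly over 0 to 100, so their SD is 100/√12 = 28.9.

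**Step 1: how far apart the two estimates can be.** Level estimate minus change estimate equals the T1 difference between arms. Its chance SD is SD × √(2/n):
- 24 per arm: √(2/24) = 0.289 SD
- 15 per arm: √(2/15) = 0.365 SD

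The chance of a T1 gap above 0.25 SD in either direction is 39% at 24 per arm and 49% at 15. With 20% dropout (19 or 12 per arm) the SD of the gap is 0.324 or 0.408 SD.

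**Step 2: what a T1 gap does.** On average a gap d carries r·d into the T3 contrast. The change contrast subtracts all of d, so it keeps −(1−r)·d. Adjustment for T1 removes both.

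**Step 3: standard errors.** In SD units:
- level: √(2/n)
- change: √(2/n) × √(2(1−r))
- T1-adjusted: √(2/n) × √(1−r²)

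| r | level, n = 24 | change, n = 24 | adjusted, n = 24 | level, n = 15 | change, n = 15 | adjusted, n = 15 |
|---|---|---|---|---|---|---|
| 0.5 | 0.289 | 0.289 | 0.250 | 0.365 | 0.365 | 0.316 |
| 0.7 | 0.289 | 0.224 | 0.206 | 0.365 | 0.283 | 0.261 |
| 0.8 | 0.289 | 0.183 | 0.173 | 0.365 | 0.231 | 0.219 |
| 0.9 | 0.289 | 0.129 | 0.126 | 0.365 | 0.163 | 0.159 |

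**Step 4: percentile points at 24 per arm.** Turning z-scores into percentiles lowers the correlation slightly, to (6/π) × arcsin(r/2): 0.483 at r = 0.5 and 0.891 at r = 0.9.
- Level: 28.87 × 0.2887 = 8.3 at every r.
- Change: 8.33 × √(2 × 0.517) = 8.5 at r = 0.5; 8.33 × √(2 × 0.109) = 3.9 at r = 0.9.
- Adjusted: 8.33 × √(1 − 0.483²) = 7.3 at r = 0.5; 8.33 × √(1 − 0.891²) = 3.8 at r = 0.9.

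**Step 5: gain from adjustment.** Adjusted over change is √((1+r)/2): 0.866 at r = 0.5 and 0.975 at r = 0.9, a reduction of 13% and 2.5%. The percentile figures give 14% and 3%. Estimating the slope costs about one percentage point, so about 2% to 13% is a fair summary. Adjusted over level is √(1−r²): a reduction of 13% at r = 0.5 and 56% at r = 0.9.

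**Step 6: what one model does.** With T1 as a covariate in a linear model, analysing T3 or the change gives the same treatment effect; in 4,000 simulated trials per setting the largest difference was rounding error. With rank methods the equivalence need not be exact.

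**The case against.** The strongest reply is that only one test is planned, and it compares changes. It is described as similar to the analysis of the primary outcomes, which also concerns differences in change. On that reading the aim is loosely worded beside a usable analysis. This stands. A reader might infer that the plan will report a level effect size next to a change test and that the two will clash, but the documents do not support that. No test of T3 level is proposed, and the effect size is unspecified rather than a level contrast. Rates of disagreement between a level test and a change test would therefore compare the planned test with one that nobody has proposed.

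Two further inferences also fail. Baseline imbalance does not pass in full into a T3 contrast; on average a fraction r of it does. And neither contrast is biased: under randomisation both have the same expected value on a linear scale.

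The advantage of change over level also depends on r. It disappears at r = 0.5 and is modest at 0.6. Finally, the aim is exploratory, and the SAP says that no sample size calculation is required.

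What the reply does not remove is that the stated question and the planned test differ in current text in both documents, that the effect size has no defined contrast, and that baseline adjustment is left open.

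**Conclusion.** The point holds as a gap in specification. The aim names T3 status, the test names change, the effect size names neither, and the T1 value is not a committed covariate. The consequences are avoidable imprecision and room to choose the reported contrast after seeing the data. They do not include bias, and the documents do not plan two competing tests.

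The precision at stake against the planned change test is small, about 2% to 13% of the standard error for r between 0.9 and 0.5. Against an unadjusted T3 contrast, should the effect size be computed that way, it runs from 13% to 56%. These figures rest on the assumed correlation, equal SDs and normal z-scores. The relative gains are the same at 15 and 24 per arm, so the conclusion does not depend on which sample size is current. Severity is low to moderate: Protocol 1.0 lists the aim as secondary, but it is exploratory everywhere else and no power is claimed for it.

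**What to change.** State one contrast in Protocol 1.0, 2.0 and 16.1 and in the SAP Exploratory Aim: the between-arm difference in T3 child weight-for-length percentile, adjusted for its own T1 value and parent BMI. In the SAP, make the T1 value a fixed covariate for this analysis instead of one to be considered.

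Take the effect size and its 95% confidence interval from that same model, for example a linear ANCOVA with a bootstrap or permutation interval. A rank-based ANCOVA can serve as the nonparametric test, but a rank test alone gives no effect on the percentile scale, so it cannot replace the model estimate. Keep group summaries of T1 and T3 as description only.

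The cost is a few sentences and one degree of freedom. T1 weight is already collected, and children without it are lost to the change analysis anyway. A smaller edit, writing change from baseline into the aim and the effect-size sentence, would also end the mismatch, but it would forgo the gain in precision.

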Training session materials include a 90-minute presentation prior to the intervention implementation and a 90-minute mid-training session in-between lesson 4 and 8. Both training sessions have been developed and pilot-tested in our preliminary feasibility study, and all enrolled EI providers participated in those sessions without attrition. On-going EI provider support will be provided by offering co-coaching the sessions when the EI providers need assistance on nutrition-specific activities. Randomly selected sessions (20%) will be observed and check whether all lesson components are consistently implemented as designed across EI providers, adapting the 5-point scale from a previous clinical trial. We will examine whether our intervention sessions fit the context of the EI services as well as the needs, expectations, and values of the EI providers, using an exit survey. Using those selected sessions, compatibility of the intervention content and activities for different levels of children's autism features and symptoms will also be examined from the observation or video-recorded sessions. EI providers and parents will be invited for a semi-structured interview at 5-month follow-up. The interviews will be audio/video recorded for transcriptions.

Three-day food record is a gold-standard assessment for dietary intake of individuals. Three 24-hour food records will be completed by parents using the NCI's Automated Self-administered 24-Hour Dietary Recall. Research assistants (RA) will provide guidance as needed. We focus on average daily dietary intakes by food groups (i.e., fruit, vegetables, grain, protein, and dairy) and daily food variety. For all children aged 2 years or older, diet quality will be determined by the Healthy Eating Index's total and sub-component scores (adequacy vs. moderation food categories). The Brief Autism Mealtime Behavior Inventory (BAMBI) will be used to assess children's mealtime behaviors. The BAMBI is a validated assessment tool that contains 18 questions and uses a 5-point Likert scale. A trained RA (single-blinded) will assess children's height and weight with a professional stadiometer and a weight scale following the standardized protocol used in previous studies. As a standard weight status assessment for birth to 36 months, weight-for-length based on the CDC growth chart will be calculated. Parent BMI will be calculated and used as a covariate in data analysis. If height and weight

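### The SAP promises recommendations for any sex differences, but nothing it plans estimates whether the Autism Eats effect differs by sex, and no trigger is set

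*SAP*

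**What the plan says.** The Sex paragraph of the SAP (under Biological variables) has three steps. First, "in addition to the primary data analyses as described above, data distributions will be analyzed by sex". Second, "We will then explore how male and female students respond to our intervention differently through qualitative interviews with selected sub-samples". Third, "Recommendations will be created to address any sex differences". No size, test, interval or error rate is attached to any step, and the purpose of the recommendations is not stated.

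Sex appears in two other places in the SAP. It is listed among potential confounders, without saying whether the parent's or the child's sex is meant. It is also one of the variables in the paragraph on demographic variation in response: "Correlation will be used to examine associations between demographic variations (age, sex, race/ethnicity, SES, and baseline weight status) outcomes of the Autism Eats", the outcomes being "food intakes, food variety, diet quality, mealtime behaviors, and weight percentile".

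The main efficacy analysis (SAP, Aim 2b) uses time as the within-subject factor and "treatment condition as a between-subject factor to examine the difference in changes between Autism Eats and EUC groups". It has no sex-by-arm term.

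**The concern.** A statement that boys and girls respond differently to Autism Eats is a statement about an interaction: the Autism Eats minus EUC difference in one sex against the same difference in the other. The plan never forms that quantity.

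- Distributions by sex mix response with whatever differences in intake or growth the sexes would show without the programme.
- The correlation concerns Autism Eats outcomes and has no EUC contrast, so it has the same weakness.
- The interviews are with parents and providers (Protocol section 5.2; SAP Table 3), because the children are at most 36 months old. The sub-samples have no stated selection rule, and the sentence takes a difference in response as given. Interviews can describe experience and acceptability; they cannot supply the missing EUC comparison.

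The plan nevertheless commits to an output, recommendations, on the strength of these sources. If the effect is the same in both sexes, any recommendation made on the ground that it differs would be wrong. Nothing written in the plan limits how often that happens.

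**Working it through.** The SAP gives no error rate for the sex analysis and no sample size calculation, so there is no figure of its own to reproduce. The question is how often a difference would appear by chance if there were none, under the triggers that a reader might supply.

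**Inputs from the documents**
- Dyads: 48, 24 per arm (Protocol sections 5.1 and 11.1), or 30 with 1:1 allocation, about 15 per arm (SAP, sample size section). Both are shown.
- Outcomes: the five food groups in Protocol section 5.2 ("fruit, vegetables, grain, protein, and dairy"), food variety, BAMBI and weight status, which makes 8. Diet quality is left out because it is scored only from age 2; including it would raise the rates.

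**Assumptions, not in the documents**
- Girls are 20-40% of the sample.
- Outcomes are normal with SD 1 and an equal between-outcome correlation of 0.3 to 0.6.
- Dyads are independent and none drop out.
- The treatment effect is identical in both sexes, with no underlying sex difference.

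**Formulas**, with g girls and b boys per arm
- Pooled boys versus girls: SE = sqrt(1/(2g) + 1/(2b)).
- Sex-by-arm difference: SE = sqrt(2/g + 2/b).
- One outcome: P(|gap| > 0.5) = 2 × [1 − Φ(0.5/SE)].
- At least one of 8: the same event for 8 equally correlated normal gaps.

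Example with g = 5, b = 19. Pooled SE = sqrt(0.100 + 0.0263) = 0.355; 0.5/0.355 = 1.41; P = 0.16. Sex-by-arm SE = sqrt(0.400 + 0.1053) = 0.711; 0.5/0.711 = 0.70; P = 0.48.

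**Gap over 0.5 SD.** For at least one of 8, the first figure is at correlation 0.3 and the second at 0.6.

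| N | g/b per arm | Pooled SE | One outcome | At least one of 8 | Sex-by-arm SE | One outcome | At least one of 8 |
|---|---|---|---|---|---|---|---|
| 48 | 5/19 | 0.36 | 0.16 | 0.70, 0.55 | 0.71 | 0.48 | 0.99, 0.97 |
| 48 | 10/14 | 0.29 | 0.09 | 0.47, 0.35 | 0.59 | 0.39 | 0.97, 0.92 |
| 30 | 3/12 | 0.46 | 0.27 | 0.89, 0.78 | 0.91 | 0.58 | 1.00, 0.99 |
| 30 | 6/9 | 0.37 | 0.18 | 0.74, 0.60 | 0.75 | 0.50 | 0.99, 0.98 |

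**Other triggers**
- Any non-zero gap: essentially 1.
- Nominal p<0.05 on any of 8: 0.30 at correlation 0.3 and 0.22 at 0.6. If the outcomes were independent it would be 1 − 0.95^8 = 0.34.
- Pooled gap over 0.8 SD on at least one of 8, N=48: 0.04-0.16.

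Dropout would enlarge every SE and so raise the rates for the fixed-size triggers. A real underlying sex difference in intake or growth would raise the pooled rates further, with no difference in treatment effect behind it.

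**The case against.** The strongest reply is that this is loosely worded exploratory prose in a pilot. In ordinary English the sentence can mean recommendations if differences are found, after exploration and interviews. The SAP itself says that evaluating outcomes belongs in a fully powered study, and the sex paragraph touches neither the feasibility benchmarks nor the main efficacy analysis.

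Much of that stands, and it rules out three stronger readings.

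- A reader might infer that the rule fires almost always and can never come out negative. The documents set no trigger, so they do not support this. It is true of the literal word *any* and nearly true of a 0.5 SD sex-by-arm gap. It is not true of a pooled 0.5 SD gap with 48 dyads (0.35-0.70) or of p<0.05 (0.22-0.30). Interviews might also filter out some apparent differences, although no filtering rule is written.
- A reader might infer that the programme would be delivered differently to boys and girls, or that the recommendations would pass into a later trial. The SAP does not say what they are for.
- A reader might take it as given that one sex will be a small subgroup. The SAP mentions the sex difference in ASD prevalence, but neither document gives a sex ratio, and children at risk or monitored for ASD are also eligible.

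The reply does not supply the missing contrast. Whatever trigger staff adopt, by-sex distributions and a correlation without EUC cannot separate different response from ordinary difference. The pilot's limited aims are a reason not to promise recommendations by sex.

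**Conclusion.** The point holds as a mismatch between what is planned and what is promised. The SAP undertakes to make recommendations about sex differences, but plans no estimate of a sex difference in the Autism Eats minus EUC effect and sets no trigger. With equal effects and no underlying sex difference, the chance of a false prompt runs from about 0.22 (p<0.05 on any of 8 outcomes) to essentially 1 (any non-zero gap) across those triggers and a 0.5 SD gap; a stricter threshold could bring it lower. The sizes rest on the assumed share of girls, the outcome correlations and the unit-SD scaling. The absence of an arm contrast by sex rests on none of them and is the same at 30 or 48 dyads. The matter is confined to an exploratory paragraph and is cheap to put right.

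**What to change.** Replace the last two sentences of the SAP's Sex paragraph with:

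> For BAMBI and fruit and vegetable intake, we will report the Autism Eats minus EUC difference in change from baseline to post-intervention by sex, and the sex-by-arm difference with its 95% confidence interval. Results by sex are descriptive and hypothesis-generating, and no sex-specific recommendation will be based on them. Parent and provider interviews will describe acceptability by child sex and will not be used as evidence of differential effect.

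Permitting a recommendation whenever the interval excludes zero would be a poor substitute. Without a fixed time point or multiplicity rule, two or three outcomes at two follow-ups give 4 to 6 intervals and a false-trigger rate of 1 − 0.95^4 = 0.19 to 1 − 0.95^6 = 0.26 if independent. Power for a true 0.5 SD interaction is only about 9-14%.

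The cost is a wording change and one extra contrast per named outcome, from data already collected. The intervals will be wide: SE about 0.6-0.7 SD with 48 dyads and 0.75-0.9 SD with 30, so half-widths of roughly 1.96 × 0.6 = 1.2 SD to 1.96 × 0.9 = 1.8 SD. The trial also gives up sex-specific recommendations.

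### The SAP's correlations of demographics with outcomes include no contrast with EUC, so they cannot show how response to Autism Eats varies with demographics

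*SAP*

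**What the plan says.** The SAP paragraph headed "Examine demographic variations in response to the Autism Eats intervention" gives a single method: "Correlation will be used to examine associations between demographic variations (age, sex, race/ethnicity, SES, and baseline weight status) outcomes of the Autism Eats". The outcomes listed are food intakes, food variety, diet quality, mealtime behaviors and weight percentile. The sentence does not fix the arm, the time point, or whether level or change is meant. A word seems to be missing before the outcomes, possibly from the PDF reading, and nothing here rests on that.

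The related places in the SAP are:

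- **Aim 2b.** The longitudinal analysis is there "to examine the difference in changes between Autism Eats and EUC groups". Its factors are time and treatment condition, with no demographic-by-treatment term.
- **Confounders.** Demographics reappear under "Potential confounding factors to be considered in the analytic models". That is adjustment, not effect modification.
- **Biological variables, sex.** Here "data distributions will be analyzed by sex", and then: "We will then explore how male and female students respond to our intervention differently through qualitative interviews with selected sub-samples". Neither step is stated as a comparison between arms.

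Protocol 16.1 contains no analysis of demographic variation in response on the efficacy outcomes.

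**The concern.** The heading asks a question about effect modification: for whom does Autism Eats work better or worse than EUC? The method answers a different one: which characteristics go with the outcome? A characteristic can predict diet, mealtime behavior or weight, or their change over five months, in children who never received the intervention. Without the EUC arm in the calculation, such a prognostic association can be reported as differential response, and a correlation near zero can be reported as uniform response. Either statement could shape who a later trial targets. The trial already randomizes a concurrent EUC arm and collects all the variables needed for the contrast.

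**Working it through.** The SAP gives no figure to reproduce on this point, so the check has two parts: what each candidate analysis estimates, and how far that could mislead.

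**1. What is estimated.** Let Y be the outcome (level or change), X a characteristic in SD units, and T = 1 for Autism Eats and 0 for EUC:

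Y = a + δT + βX + γTX + error.

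Here β is what X predicts under EUC and γ is differential response.

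| Analysis | Slope estimated |
|---|---|
| Autism Eats arm only | β + γ |
| Both arms pooled, 1:1 | β + γ/2 |
| Autism Eats minus EUC | γ |

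Only the last row isolates γ. This holds for level and for change; using change alters what β means but does not remove it.

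**2. Inputs.** Dyads per arm: 15 (SAP, N=30 at 1:1) or 24 (Protocol 5.1). Dropout: "We aim < 20% dropout due to study withdrawal", so at 20% about 12 (15 × 0.8) or 19 (24 × 0.8 = 19.2) remain. The documents give no correlations, no significance threshold and no type of coefficient. All correlations below are therefore assumptions, Spearman is used, and flagged means two-sided p<0.05.

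**3. Reading A: change in the Autism Eats arm, γ = 0.** Correlating a baseline value with its own change, at equal variances and test-retest correlation r, gives an expected correlation of −√((1−r)/2). That is −0.22, −0.39 and −0.50 for r = 0.9, 0.7 and 0.5. It applies to baseline weight status with weight percentile. Share flagged (bivariate normal, 40,000 simulated trials per case):

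| r | n=15 | n=24 | n=12 | n=19 |
|---|---|---|---|---|
| 0.9 | 0.117 | 0.165 | 0.099 | 0.139 |
| 0.7 | 0.270 | 0.424 | 0.212 | 0.345 |
| 0.5 | 0.439 | 0.663 | 0.345 | 0.547 |

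For the other pairs the result depends on how strongly the characteristic predicts change under EUC:

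| Correlation with such change | n=15 | n=24 |
|---|---|---|
| 0 | 0.053 | 0.050 |
| 0.1 | 0.065 | 0.073 |
| 0.2 | 0.100 | 0.144 |
| 0.3 | 0.174 | 0.272 |

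**4. Reading B: outcome level in the Autism Eats arm, γ = 0.** At prognostic correlations of 0.3 and 0.5 the share flagged is 0.176 and 0.434 (n=15), or 0.270 and 0.664 (n=24). Pooling both arms raises it: with Pearson and an assumed 0.5 SD treatment effect, 0.349 and 0.802 at 15 per arm, and 0.527 and 0.952 at 24.

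**5. The contrast with EUC.** Model: follow-up on baseline, arm, X and arm × X, with an assumed baseline coefficient of 0.5 (residual variance 0.75).

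- *No modification, normal outcomes:* the interaction is flagged in 0.044–0.054.
- *No modification, lognormal outcomes, slope 0.5:* 0.092 (15 per arm) and 0.097 (24) on the raw scale; 0.037 at both sizes on ranks. The scale therefore needs to be fixed in advance.
- *Precision:* the half-width is approximately t(2n−5) × √0.75 × √(2/(n−3)). At n=15: 2.060 × 0.866 × 0.408 = 0.73. At n=24: 2.017 × 0.866 × 0.309 = 0.54. Simulation gives the same values, and 0.85 and 0.62 at 12 and 19 per arm.
- *Sex:* with an assumed 50% or 80% of one sex, the half-width is 1.31 or 1.65 SD at 15 per arm, and 1.01 or 1.25 SD at 24.
- *Power for a slope difference of 0.5:* 24–33% at 15 per arm and 40–51% at 24, depending on scale and residual variance.

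These figures treat dyads as independent. The protocol plans 30 providers for 48 dyads (1.6 per provider), so some sharing is expected there.

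**The case against.** The strongest reply is about weight. This is one exploratory paragraph in a pilot that says outcome evaluation belongs in a fully powered trial. The sentence promises only to examine associations, which correlation does, and no threshold, claim or decision is attached. On the most natural reading, change in Autism Eats children, most pairs behave properly unless a characteristic predicts change under EUC, and the documents give no sign of how strongly any does. The proposed contrast is imprecise: with 15 per arm and 80% of one sex, three children per arm are of the other sex. All of this stands, and it limits the priority. It does not rebut the point, because low precision does not turn a correlation into a measure of differential response, and the heading does say response.

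A reader might also infer that the SAP will act on these correlations, because it says "Recommendations will be created to address any sex differences". The documents do not support that. The sentence closes the separate paragraph on sex, after the distributions by sex and the interviews, and is not tied to the correlation paragraph.

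**Conclusion.** The point holds as a mismatch between question and method. On any reading of arm, level or change, the stated correlations cannot separate prognosis from differential response, and no other analysis in the documents supplies the missing contrast. The conclusion is the same at 15 or 24 per arm.

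Its size is modest and conditional. On the change reading, only baseline weight status with weight percentile is inflated without a further assumption (about 12–44% or 17–66% flagged, for assumed r of 0.9 to 0.5). Inflation elsewhere requires that the characteristic predicts change under EUC, or that level is meant.

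Three stronger inferences are not supported:

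- **That false signals run through all the pairs.** They need not. Five characteristics by five named outcomes gives 25 pairs, and that is itself an undercount, since food intakes cover several food groups and the Healthy Eating Index has sub-scores.
- **That real modification would generally be missed.** A 5% flag rate arises when the EUC slope is 0.5 and the Autism Eats slope is exactly 0, which is a constructed case. The interaction test also usually misses that difference at 15 per arm and misses it about half the time or more at 24.
- **That the efficacy comparison is harmed.** The between-arm analysis in Aim 2b does not use these correlations.

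**What to change.** Replace the correlation sentence with wording along these lines:

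> For a short pre-listed set of outcomes, the follow-up value will be modelled on its baseline value, arm, the characteristic and arm-by-characteristic, in children from both arms, one characteristic at a time. The scale (raw or rank) is fixed in advance for each outcome. Where the characteristic is the outcome's own baseline value, it enters once. Standard errors will allow for dyads sharing an EI provider where that occurs. Interaction estimates with 95% confidence intervals will be reported as exploratory, without significance claims. An interval that includes zero will not be read as uniform response.

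Weight percentile would be modelled at 5 months only, because Table 4 collects it at T1 and T3. The grouping of race/ethnicity should be stated beforehand.

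Cost: a short SAP paragraph and no new data. The downside is the wide intervals shown above, before any allowance for clustering. They are wider still for sex and race/ethnicity, and for diet quality, which Protocol 5.2 scores only from age 2. Rank-scale interactions are also harder to interpret.

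Minimum alternative, close to one line: keep the correlations; state the arm, time point and level or change; retitle them *prognostic associations*; and draw no conclusion about differential response.
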